3.2 Power for analysis of key secondary variables

Not applicable.

4 Change to protocol specified analyses

Not applicable.

5 Appendix

5.1 Imputation rules

5.1.1 Study drug

The following rule should be used for the imputation of the dose end date for a given study treatment component:

Scenario 1: If the dose end date is completely missing and there is no EOT page and no death date, the subject is considered as on-going:

The subject should be treated as on-going and the cut-off date should be used as the dose end date.

Note: Scenario 1 should not be applicable for final CSR. All subjects should have EOT page complete before the Database lock for Final CSR

Scenario 2: If the dose end date is completely or partially missing and the EOT page is available:

Case 1: The dose end date is completely missing, and the EOT completion date is complete, then this latter date should be used.

Case 2: Only Year(yyyy) of the dose end date is available and yyyy < the year of EOT date:

Use Dec31yyyy

Case 3: Only Year(yyyy) of the dose end date is available and yyyy = the year of EOT date:

Use EOT date

Case 4: Both Year(yyyy) and Month (mm) are available for dose end date, and yyyy = the year of EOT date and mm < the month of EOT date:

Use last day of the Month (mm)

All other cases should be considered as a data issue and the statistician should contact the data manager of the study.

After imputation, compare the imputed date with start date of treatment, if the imputed date is < start date of treatment:

Use the treatment start date

Subjects with missing start dates are to be considered missing for all study treatment component related calculations and no imputation will be made. If start date is missing then end-date should not be imputed.

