6.1 Study treatment

For this study, the investigational drugs are LAG525 and spartalizumab (PDR001). The study treatment was defined as LAG525 and spartalizumab or LAG525 with or without spartalizumab in combination with carboplatin. With protocol amendment 3, enrollment to Arm 1 (LAG525 + spartalizumab) was prematurely closed. Subsequent enrolled participants will be randomized to either Arm 2 (LAG525 + spartalizumab + carboplatin) or Arm 3 (LAG525 + carboplatin).

All drugs will be administered as infusion.

Infusion must take place in a facility with appropriate resuscitation equipment available at the bedside and a physician readily available during the period of drug administration. The participant should be closely observed for potential infusion-related reactions including rigors, chills, wheezing, pruritus, flushing, rash, hypotension, hypoxemia, and fever and the vital signs should be monitored more frequently if clinically indicated, during infusions and for at least 2 hours after the last infusion for the first 2 cycles. The same close observation may be applied for the subsequent cycles if medically indicated.

All dosages prescribed and administered to participants and all dose interruptions and changes during the study must be recorded on the appropriate electronic Case Report Form (eCRF) page.

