6.1.1.2 LAG525 and LAG525 + spartalizumab administration

LAG525 and spartalizumab will be administered via i.v. infusion over 30 minutes once every 3 weeks. Infusions of each antibody can be extended to up to 2 hours if clinically indicated.

For participants who receive both drugs, they will be administered separately in the same fashion with at least a 30-min break between the two antibody infusions.

Both study drugs may be infused using the same i.v. access site. LAG525 will be given first followed by spartalizumab. The same administration sequence must be followed for all participants, i.e., LAG525 is infused first. If an infusion reaction occurs after administration of LAG525, the subsequent spartalizumab infusion must be delayed until it is safe for the participant to receive spartalizumab based on the clinical judgement of the investigator. The delay between LAG525 and spartalizumab infusions can be up to 4 hours if clinically indicated. If spartalizumab cannot be administered safely within 4 hours after LAG525 administration, the dose must be omitted.

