6.1.1.3 Carboplatin administration

Carboplatin will be administered every three weeks via i.v. infusion over 15 to 60 minutes once LAG525 and spartalizumab infusions are completed. A break of 30 minutes must be observed between any infusions. Any pre-medications should be administered as per local standard practice.

The dose of carboplatin will be adjusted in order to not exceed 900 mg corresponding to a GFR (based on the Calvert formula) capped at 125 mL/min FDA guidance 2010.

Doses subsequent to the initial dose administered at Cycle 1 Day 1 should be adjusted according to the local prescribing information for carboplatin.

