Study drug	Definition of last date of exposure of study drug	Example
------------	---	---------

LAG525 spartalizumab carboplatin	The planned end date of the last cycle in which the last non-zero dose of the investigational drug was last administered (i.e last date of administration + (planned interval duration-1day)) Note : If the subject died or was lost to follow-up before the derived last date, the last date of exposure to investigational drug is the date of death or the date of last contact, respectively. If the derived last date of exposure goes beyond the data cut-off date, it should be truncated to the date of data cut-off.	In a once every 3 weeks administration, the last date of exposure is the date of administration in the last cycle + 20 days
--	---	---

Summary of duration of exposure of LAG525, spartalizumab and carboplatin will include categorical summaries based on 21-day intervals (< 3 weeks, at least 3 weeks, at least 6 weeks, etc.) and using descriptive statistics (mean, standard deviation etc).

Cumulative dose

Cumulative dose of a study treatment is defined as the total dose given during the study treatment exposure and will be summarized for each of the study treatment components.

The **planned cumulative dose** for a study treatment component refers to the total planned dose as per the protocol up to the last date of investigational drug administration.

The **actual cumulative dose** refers to the total actual dose administered, over the duration for which the subject is on the study treatment as documented in the 'Study treatment – LAG525/PDR001/carboplatin' eCRF pages.

For subjects who did not take any drug component the cumulative dose for that component is by definition equal to zero.

For LAG525 and spartalizumab, the planned cumulative dose and actual cumulative dose will be expressed in mg.

For carboplatin, they will be expressed as calculated AUC (mg/mL x min). To that end the prescribed / administered dose in mg will be used to calculate the AUC using Calvert's formula based on the derived GFR value. Calvert's formula is given as:

- Carboplatin dosage (mg) = AUC (mg/mL x min) x [GFR (mL/min) + 25]

And the back-calculation for AUC is

- AUC (mg/mL x min) = Carboplatin dose (mg) / [GFR (mL/min) + 25]

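### SAP 5.1.1 imputes missing dose end dates as if dosing were continuous, although every drug is a same-day infusion; where the rule runs, it can add days to months of false exposure time.

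*SAP*

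**What the plan says.** SAP 5.1.1 (Study drug) gives the imputation rule for the dose end date of each study treatment component:

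- **Scenario 1** (end date missing, no EOT page, no death date): "The subject should be treated as on-going and the cut-off date should be used as the dose end date". A note says that this should not arise for the final CSR.
- **Scenario 2, Case 1** reads as follows: "The dose end date is completely missing, and the EOT completion date is complete, then this latter date should be used".
- In **Case 2** (year alone known, and earlier than the EOT year): "Use Dec31yyyy".
- **Case 3** (only the year known, same as the EOT year): the EOT date.
- **Case 4** (year and month known, month earlier than the EOT month in the same year): the last day of that month.

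Other patterns go to the data manager. The imputed date is checked only against the treatment start date. If the start date is missing, no end date is imputed.

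The dosing is intermittent. Protocol 6.1: "All drugs will be administered as infusion". Protocol 6.1.1.2: "LAG525 and spartalizumab will be administered via i.v. infusion over 30 minutes once every 3 weeks", extendable to 2 hours. Protocol 6.1.1.3: "Carboplatin will be administered every three weeks via i.v. infusion over 15 to 60 minutes".

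**The concern.** An end date later than the start date makes sense for a drug taken daily over a recorded interval. An infusion of 15 minutes to 2 hours starts and ends on the same day. Because 5.1.1 imputes only when the start date is known, the correct value is already available, and the rule replaces it with a later one.

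The date of last administration feeds duration of exposure, dose intensity (DI) and relative dose intensity (RDI) in SAP 2.4.1. It also sets the 30-day on-treatment period and the 150-day reporting windows in SAP 2.1.1. If the imputed date is used there, exposure is too long, DI and RDI are too low, and some post-treatment adverse events could be counted as treatment-emergent.

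The safeguards are uneven. SAP Table 5-2, for adverse events and concomitant medications, caps imputed end dates at death, cut-off and consent withdrawal, and compares them with the start date of the same record. SAP 5.1.1 does neither. SAP 2.1.1 bars completely imputed dates from the last contact date and names the cut-off substituted for a missing dose end date as an example. No such bar is stated for exposure or the safety windows.

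**Working it through.** **Inputs.** SAP Table 2-5: LAG525 400 mg on 13Jun, 04Jul and 25Jul2018, then permanent discontinuation recorded on 15Aug2018. SAP Table 2-3: last date of exposure = last administration + 20 days. Planned dose intensity is 400 mg/cycle.

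**Formulas (SAP 2.4.1).** Exposure days = (last administration + 20 days) − first administration + 1. Cycles = days / 21. DI = 1200 mg / cycles. RDI = DI / 400.

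**Reproducing the SAP's figure.** 25Jul + 20 days = 14Aug2018. From 13Jun to 14Aug inclusive is 63 days, or 3 cycles. DI = 1200/3 = 400 mg/cycle and RDI = 100%, as Table 2-5 states.

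**What the rule would give.** Assume that the 25Jul2018 record has no complete end date and that the imputed date is used as last administration. No truncation is applied in this table.

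| Imputed date | Days added | Exposure (days) | Cycles | RDI | On-treatment period ends |
|---|---|---|---|---|---|
| 25Jul2018 (same day, correct) | 0 | 63 | 3.00 | 100% | 24Aug2018 |
| EOT 7 days after last dose (01Aug2018) | 7 | 70 | 3.33 | 90% | 31Aug2018 |
| EOT on 15Aug2018 | 21 | 84 | 4.00 | 75% | 14Sep2018 |
| EOT after a 12-week interruption (17Oct2018) | 84 | 147 | 7.00 | 42.9% | 16Nov2018 |
| Case 4, month end (31Jul2018) | 6 | 69 | 3.29 | 91.3% | 30Aug2018 |
| Case 2, 31 December (EOT in 2019) | 159 | 222 | 10.57 | 28.4% | 30Jan2019 |

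Worked line for EOT on 15Aug2018: 15Aug + 20 days = 04Sep; 04Sep − 13Jun + 1 = 84 days; 84/21 = 4 cycles; 1200/4 = 300 mg/cycle; 300/400 = 75%.

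The EOT dates are assumptions. Seven days is the limit in Protocol 16.3.4.2. The EOT column of Protocol Table 8-1 gives no day window. Twelve weeks is the longest antibody interruption in Protocol 6.5.1.1.

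**Scenario 1.** With the cut-off of 23Aug2018 from SAP Table 2-4, the end date moves 29 days. Truncation at the cut-off limits exposure to 72 days against 63, so 9 days are added.

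**A component stopped early.** Protocol 6.1.5 lets the investigator stop carboplatin after 6 cycles. Its last dose is then 5 × 21 = 105 days after the first. If the antibodies run k cycles and the overall EOT date is 7 days after their last dose, the days added to carboplatin exposure are (k − 1) × 21 + 7 − 105: 49 for k = 8, 91 for k = 10 and 133 for k = 12. If 5.1.1 means the drug-specific disposition page, these figures shrink.

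**Range.** Case 4 adds 0 to 30 days and Case 2 adds 0 to 364. The total dose given stays at 1200 mg throughout.

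**The case against.** The strongest reply is that the rule may never run. The SAP's dosing tables carry one combined start/end date per record, and with a single date the end cannot be missing while the start is known. That keeps the frequency open but does not clear the rule: 5.1.1 treats a missing start and a missing end as separate events, and the last contact rule in SAP 2.1.1 names a missing dose end date. The sponsor evidently expects such records.

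Second, SAP 2.1.1 defines last administration by a nonzero dose given and entered on the eCRF, and runs the on-treatment period from the last actual administration. Nothing says that a 5.1.1 date replaces it. This stands, and it makes the size conditional. But 5.1.1 does tie dose dates to component-level calculations, and if the imputed date feeds none of them the rule has no purpose.

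Third, limits exist. Exposure is truncated at death, last contact and cut-off. Scenario 1 should not occur in the final CSR. An EOT visit on schedule adds at most 7 days. A large Case 2 shift for an antibody is hard to reach, because an interruption beyond 12 weeks ends that drug, so another component would usually have to continue. These points stand. They reduce the likely size but do not make the imputed date correct.

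Fourth, the amended SAP serves a close-out report on safety and PK with no inferential analysis planned (SAP 1). That bears on priority, not on whether the rule fits.

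**Conclusion.** The concern holds in a conditional form. SAP 5.1.1 does not suit same-day infusions, and where it runs past the infusion day it supplies a wrong date. If that date is used as last administration, it adds false exposure time and lowers DI and RDI. It lengthens the on-treatment window by the same number of days when the affected component was the last drug given. In the Table 2-5 example the plausible EOT dates give 70 days and 90%, or 84 days and 75%, against 63 days and 100%.

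This rests on two assumptions that the documents do not settle: that some records lack an end date, and that the imputed date replaces the recorded administration date.

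A reader might infer more, and the documents do not support it:

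- **That the rule creates false dosing.** It adds time only; cumulative mg does not change.
- **That the error is always weeks to months.** It can be a few days, or none.
- **That efficacy is at risk.** ORR and PFS do not use this date, and completely imputed dates are barred from OS censoring.
- **That this trial's safety tables are already distorted.** No affected record is shown.

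The change is worth making because the possible bias falls on the descriptive exposure and safety tables that the close-out report serves, and removing it is nearly free.

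**What to change.** Replace Scenarios 1 and 2 of SAP 5.1.1 with wording such as:

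> *If the end date of an infusion record is missing, or is partial and consistent with the start date, set it to that record's start date. If a partial end date conflicts with the start date, query it.*

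The query matters: overwriting every partial date would hide a real conflict between a recorded month or year and the start date.

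Add one sentence to SAP 2.1.1 and 2.4.1 stating that last administration, duration of exposure and the 30-day and 150-day safety windows use the infusion (start) date.

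Under this rule the Table 2-5 patient stays at 63 days, 3 cycles and RDI 100%, with the on-treatment period ending 24Aug2018. The cost is SAP wording and simpler programming. No new data are needed beyond answers to any queries.

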5.1.2 AE, ConMeds and safety assessment date imputation

Table 5-1 Imputation of start dates (AE, CM) and assessments (LB, EG, VS)

Missing Element	Rule
day, month, and year	
 No imputation will be done for completely missing dates
day, month	
 If available year = year of study treatment start date then 
 If stop date contains a full date and stop date is earlier than study treatment start date then set start date = 01JanYYYY Else set start date = study treatment start date. If available year > year of study treatment start date then 01JanYYYY If available year < year of study treatment start date then 01JulYYYY
day	
 If available month and year = month and year of study treatment start date then 
 If stop date contains a full date and stop date is earlier than study treatment start date then set start date= 01MONYYYYY. Else set start date = study treatment start date. If available month and year > month and year of study treatment start date then 01MONYYYYY If available month and year < month year of study treatment start date then 15MONYYYYY

Table 5-2 Imputation of end dates (AE, CM)

Missing Element	Rule (* = last treatment date plus 30 days not > (death date, cut-off date, withdrawal of consent date))
day, month, and year	
 Completely missing end dates (incl. ongoing events) will be imputed by the end date of the on-treatment period* 
After imputation, compare the imputed end date with the start date of that specific record: if imputed end date before start date then impute to start date

day, month	
 If partial end date contains year only, set end date = earliest of 31DecYYYY or end date of the on-treatment period* (if same year as partial end date)

Missing Element	Rule (* = last treatment date plus 30 days not > (death date, cut-off date, withdrawal of consent date))
day	
• If partial end date contains month and year, set end date = earliest of last day of the month or end date of the on-treatment period* (if same month and year as partial end date)

Any AEs and ConMeds with partial/missing dates will be displayed as such in the data listings.

Any AEs and ConMeds which are continuing as per data cut-off will be shown as 'ongoing' rather than the end date provided.

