The date of last administration of study treatment is derived as the last date when a nonzero dose of any component of study treatment was administered as per ‘Study treatment – LAG525/PDR001/carboplatin’ eCRF pages. (Example: if the last spartalizumab dose is administered on 15-Apr-2018, and the last dose of LAG525 is administered on 17-Apr-2018, then the date of last administration of study treatment is on 17-Apr-2018).

Study day

The study day, describes the day of the event or assessment date, relative to the reference start date.

The study day is defined as:

- The date of the event (visit date, onset date of an event, assessment date etc.) – reference start date + 1 if event is on or after the reference start date;
- The date of the event (visit date, onset date of an event, assessment date etc.) – reference start date if event precedes the reference start date.

The reference start date for safety assessments (e.g. adverse event onset, laboratory abnormality occurrence, vital sign measurement, dose interruption, ECOG performance status, PK etc.) is the start of study treatment.

The reference start date for all other, non-safety assessments (i.e., tumor assessment, survival time, disease progression, tumor response) is the date of randomization.

The study day will be displayed in the data listings. If an event starts before the reference start date, the study day displayed on the listing will be negative.

Note: Some measurements may belong to safety measurement and to efficacy measurement (‘death’ is an efficacy endpoint, but it can also be included in the safety analysis). For safety, the ‘study day’ will be calculated relative to start of study treatment, while for efficacy overall survival will be derived relative to randomization date.

Time unit

A year length is defined as 365.25 days. A month length is 30.4375 days (365.25/12). If duration is reported in months, duration in days will be divided by 30.4375. If duration is reported in years, duration in days will be divided by 365.25.

Baseline

For efficacy evaluations, the last non-missing assessment, including unscheduled assessments on or before the date of randomization is taken as “baseline” value or “baseline” assessment.

For safety evaluations, the last available assessment on or before the date of start of study treatment is taken for “baseline” assessment.

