In case time of assessment (e.g. pre-dose ECG) and time of treatment start is captured, the last available assessment before the treatment start date/time is used for baseline.

For safety parameters (e.g ECGs), where study requires multiple replicates per time point, the average of these measurements would be calculated for baseline (if not already available in the database).

In rare cases where multiple measurements meet the baseline definition, with no further flag or label that can identify the chronological order, then the following rule should be applied:

- If values are from central and local laboratories, the value from central assessment should be considered as baseline.
- If multiple values are from the same laboratory (local or central) or collected for ECGs or vital signs, then the value closest to normal should be considered as baseline.

If subjects have no value as defined above, the baseline result will be missing.

On-treatment assessment/event and observation periods

For adverse event reporting the overall observation period will be divided into three mutually exclusive segments:

1. **pre-treatment period:** from day of subject’s informed consent to the day before first administration of study treatment
2. **on-treatment period:** from date of first administration of study treatment to 30 days after date of last actual administration of any study treatment (including start and stop date)
3. **post-treatment period:** starting at day 31 after last administration of study treatment.

If dates are incomplete in a way that clear assignment to pre-, on-, post-treatment period cannot be made, then the respective data will be assigned to the on-treatment period. Refer to [Section 5.1.2](#) for imputation rules concerning AE start and stop dates.

For other safety data, the on-treatment period will start from the day after the date of first administration of study treatment, unless the time of assessment and time of treatment start is available on the day of study treatment start. For data where time of assessment (e.g. ECGs) and time of treatment start are captured, data collected on the day of first administration of study

treatment at a time before (after respectively) the time of first administration of study treatment will be considered on the pre-treatment period (on the on-treatment period respectively).

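### SAP Table 5-1 dates partially dated early lab and vital-sign results to Day 1, which the SAP counts as baseline, not on-treatment, for these data

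*SAP*

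**What the plan says.** SAP 5.1.2, Table 5-1, gives one partial-date rule for several kinds of record. Its title begins "Imputation of start dates (AE, CM) and assessments (LB, EG, VS", so it covers adverse events and concomitant medications as well as labs, ECGs and vital signs.

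- Day missing: "If available month and year = month and year of study treatment start date then" the date becomes treatment start, unless a complete stop date falls earlier. The instruction is "Else set start date = study treatment start date".
- Day and month missing: the same outcome under "If available year = year of study treatment start date then".
- Whole date missing: "No imputation will be done for completely missing dates".

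SAP 2.1.1 then sets the periods. For adverse events the on-treatment period includes the day of first dose. For the rest: "For other safety data, the on-treatment period will start from the day after the date of first administration of study treatment". The exception is where assessment and dosing times are captured; Day 1 data are then split by time, with ECGs as the example. On baseline: "For safety evaluations, the last available assessment on or before the date of start of study treatment is taken".

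The adverse-event text of SAP 2.1.1 adds that, when incomplete dates prevent a clear assignment, "then the respective data will be assigned to the on-treatment period". Protocol 12.5.2 states the same default for safety data generally and starts the on-treatment period on the day of first dose. SAP Section 4 lists no change from the protocol's analyses.

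**The concern.** The same imputed date has opposite effects on two kinds of record. An adverse event moved to Day 1 stays on-treatment, so the rule is cautious. A lab or vital sign moved to Day 1 falls one day before its on-treatment period opens and inside the baseline window.

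The early-termination clause offers no escape: it needs a stop date, and an assessment has none (Table 5-2 deals with end dates for adverse events and concomitant medications only).

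The outputs at stake are the worst post-baseline grade and shift tables in SAP 2.9.3 and the on-treatment vital-sign summaries in SAP 2.9.4.2. Protocol Table 8-1 schedules hematology, chemistry and vital signs at Cycle 1 Days 8 and 15, and cardiac troponin at Cycle 1 Day 15. These first-cycle visits are the ones that the rule can reach.

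**Working it through.** The documents give no count of partial assessment dates, so there is no stated figure to reproduce. The check applies the rules to dates.

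**Worked case.** First dose 13Jun2018 (the start date in the SAP's own exposure examples), day missing, no clock times.

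| True date | Study day | Imputed date | Lab or vital sign | Adverse event |
|---|---|---|---|---|
| 20Jun2018 | 8 | 13Jun2018 | not on-treatment | on-treatment |
| 27Jun2018 | 15 | 13Jun2018 | not on-treatment | on-treatment |
| 04Jul2018 | 22 | 01Jul2018 | on-treatment | on-treatment |

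**Share of records moved, if the date is partial.** Assumptions: start dates uniform over the 365 days of one non-leap year, visits on their nominal day, no clock times.

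Day missing: a Day D record is moved when it falls in the same calendar month as first dose. A month of L days has L − (D − 1) such start dates, or none if that is negative. Up to Day 29 every month has zero or more, so the share is [365 − 12(D − 1)] / 365.

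- Day 8: (365 − 84)/365 = 281/365 = 77%
- Day 15: (365 − 168)/365 = 197/365 = 54%
- Day 22: (365 − 252)/365 = 113/365 = 31%
- Day 29: (365 − 336)/365 = 29/365 = 8%
- Day 43 and later: 0%

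Day and month missing: a record is moved when it falls in the same calendar year, so the share is [365 − (D − 1)] / 365.

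- Day 8: 358/365 = 98%
- Day 43: 323/365 = 88%
- Day 57: 309/365 = 85%

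An adverse event on the same dates stays on-treatment in every case: 0% moved.

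**ECGs.** Protocol 8.4.2 schedules central ECGs at Cycle 1 Day 1, Cycle 3 Day 1 (Day 43) and end of treatment. With only the day missing, no scheduled on-study central ECG after Day 1 can fall in the start month. Local single ECGs are outside the ECG summaries (SAP 2.9.4.1). That leaves unscheduled ECGs, early end-of-treatment ECGs and year-only dates.

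**Does a moved value become the baseline?** Where several values qualify with no order flag, SAP 2.1.1 prefers central to local and, within one source, the value closest to normal. A moved Day 8 chemistry result therefore competes with the Cycle 1 Day 1 result and may lose. Troponin differs: Table 8-1 shows it at screening and Cycle 1 Day 15 but not at Cycle 1 Day 1. A Day 15 troponin moved to Day 1 would be the latest value up to treatment start and would displace screening as baseline.

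**Under the protocol's rule.** If partial lab and vital-sign dates go to the on-treatment period by default, as in protocol 12.5.2, the share lost is 0% at every visit.

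**The case against.** The strongest reply is that the protocol already protects these records. Its default sends unclear dates to the on-treatment period for all safety data. If that default governs, nothing is lost. This stands in part: the loss follows from one of two rules that the SAP does not reconcile. It does not dispose of the point. Once Table 5-1 supplies a full date, the assignment no longer looks unclear to a programmer. The SAP's own version of the default sits in its adverse-event text and points to 5.1.2 only for adverse-event start and stop dates.

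Second, data handling should keep such records rare. Most labs are run centrally, a local test should have a parallel central sample (protocol 8.4.1), and missing values are queried (protocol 11.2). This also stands and is why the point is minor. Troponin is tested locally, so the central-laboratory safeguard does not cover it.

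A reader might go further in three ways that the documents do not support:

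- That the rule always hides toxicity. The closest-to-normal tie-break often keeps an abnormal moved value from becoming baseline, and a moved value that wins can enlarge later shifts. Genuine screening or pre-dose samples with a missing day are correctly kept off treatment by the same rule. Toxicity reported as an adverse event is kept.
- That records with no date at all are moved. Table 5-1 leaves them alone.
- That ECG summaries are seriously affected. The clock-time exception and the ECG schedule largely spare them.

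**Conclusion.** The point holds for labs and vital signs with a partial date matching the calendar month of first dose (or only the start year) and no usable clock time. For a post-dose record of this kind, SAP Table 5-1 and SAP 2.1.1 read together give a result contrary to protocol 12.5.2, and SAP Section 4 does not declare the difference.

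The conditional size is large at the first two post-dose visits (77% at Day 8 and 54% at Day 15 when the day is missing). It rests on evenly spread start dates, nominal visit days and no clock times. The absolute size cannot be stated, because the number of partial dates is not given; it is probably small and may be nil. This is a minor drafting correction. It does not show that early toxicity was in fact lost.

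**What to change.** Limit the treatment-start-date rule in Table 5-1 to adverse events and concomitant medications. For labs, ECGs and vital signs with a partial date, assign the period by the recorded visit label:

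- screening and pre-dose Cycle 1 Day 1 records stay pre-treatment;
- later visits are on-treatment and cannot serve as baseline;
- where no visit label resolves it, use the protocol 12.5.2 on-treatment default.

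A simpler patch, dating every doubtful assessment to the day after first dose, would create the opposite error. Screening runs from Day -21, so many screening samples fall in the month of first dose: under the same uniform assumption, (365 − 12 × 10)/365 = 245/365 = 67% of samples taken 10 days before first dose. That patch would count them as on-treatment and bar them from baseline.

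The cost is a short addition to Table 5-1 and a small amount of extra programming.
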